5.5 Discontinuation and Withdrawal

Participants are free to discontinue their participation in the study at any time, without prejudice to further treatment. Participants who discontinue from the study will always be asked about the reason(s) for their discontinuation and about the presence of any adverse events. If possible, they will be seen and assessed by an

Investigator and complete the withdrawal of informed consent procedure (see Appendix B; PICF). Where participants are not willing to continue any research assessments, they will be considered withdrawn from the study. Adverse events will be followed up until resolution, the adverse event stabilises, or the participant is lost to follow up.

Participant discontinuation criteria

Participants will be discontinued from participating in the study in the following circumstances and, if in need, be referred to their primary medical officer

1. Participants who develop any complications during the study
2. Participants who become too vulnerable or fragile during the study
3. Participants who miss more than 3 weeks of the treatment sessions
4. Participants who do not have a treating team

Discontinuation of parts of this study or the entire study will be considered if new information about reconsolidation therapy becomes known to the researchers.

Escalation procedure

If a participant develops a known (or previously undocumented) adverse reaction to the treatment during the study, clinical and research staff will refer to the *Recognising and Responding to Physiological deterioration SOP* which will include some or all of the following:

- Appropriate and timely medical care is provided by trained and qualified staff. If required, the emergency services (Queensland Ambulance Services – QSA) and UniSC security are contacted immediately.
- Attending registered nurse will monitor physiological signs and symptoms on initial session.
- If the ambulance service is not required, the participant will be referred for consultation with their GP and their participation from the study will be withdrawn.
- If the ambulance service is required for immediate medical admission, the clinical and research staff will supply relevant patient information to assist with participant treatment and monitoring.
- Escalation, either hospital admission or GP referral, will be coordinated by the Registered Nurse with support from technical and research staff of the Thompson Institute. Any escalation will require an immediate (within 1-day) staff meeting, to debrief, check on staff welfare, review processes and procedures, and ensure all appropriate adverse event documentation is completed in line with stipulations in section 10 (safety measures).

If a participant's mental health condition significantly deteriorates during the study, the clinical and research staff will refer to the *Recognising and Responding to Deterioration of Mental state – Operating Procedure, and Escalation of Care Guidelines* which will include some of all of the following:

- Assessment of mental health condition (Mental State Examination by qualified clinician)
- Clinician assessment of indicators and signs of deterioration including:
 - any reported changes,
 - signs of distress,
 - loss of touch with reality or consequence of behaviours,
 - loss of function,
 - dissociation
 - elevated risk to self, others or property.
- Call 000 for emergency response
- De-escalation and management of increased physical aggression
- Contact made with participants GP and other members of treating team
- Referral to acute mental health services as required

Withdrawal criteria

Participants may withdraw at any time during the study. A participant will be considered 'withdrawn' from the study in cases where all involvement is ceased. A participant will be withdrawn in the following cases:

1. Revocation of consent
2. The site PI believes that it is in the best interest of the participant to be withdrawn.

Should either of the above situations take place, withdrawal will occur immediately.

5.6 Safety Measures

The TI/NPRC has Standard Operating Procedures (SOP) in place to manage adverse and severe adverse events, complaints and feedback and medical emergencies. The PI is required to ensure all study staff are aware of the definitions and procedures in the SOP. Summary details of the SOP can be found in Appendix I.

5.7 Study Risks

Several risks, inconveniences and potentials for distress have been identified as a part of this study. As such, the researchers have employed methods to mitigate these risks, which are outlined below. Prior to study commencement, a risk assessment meeting will be conducted with key study personnel (CIs, AIs and study-specific new hires) to comprehensively identify risks and management and mitigation strategies. Identified risks associated with this study will be added to the site-specific project risk registers. The TI/NPRC will utilise UniSC's established risk framework inclusive of a risk matrix (Likelihood: Almost Certain – Rare; Consequences: Catastrophic – Insignificant) to calculate both inherent and residual risks. Further guiding policies that aid in determining risk likelihood and consequence, as well as UniSC's Risk and Compliance Manual, will be fundamental resources for this project.

Potential harms: Propranolol use

There is risk of minor physical side effects associated with propranolol medication as outlined in the RPIS and PICF (see Appendix A and B). Potential side effects include lowered blood pressure, nausea, dizziness, and fatigue.

Potential harms: Economic

The participants may incur costs in accessing transport to and from the Thompson Institute. If employed, participants may forgo hours worked at employment to attend treatments.

Potential harms: Diagnostic, psychological, cognitive measures

Recruitment of participants who might have undiagnosed disorder which is marked as exclusion criteria (e.g., asthma, diabetes, severe psychiatric condition).

Participants will be asked to complete several questionnaires assessing their behaviours, cognitive function, and emotions and feelings. Whilst there are no anticipated risks associated with participation in this research, we do acknowledge the possible anxiety or other psychological distress which may arise when these topics are discussed.

Potential harms: Discomfort and inconvenience

Participants may feel anxious or distressed about the treatment because of it not being commonly used practice in clinical setting. Participants may experience stress, distress, discomfort and/or anxiety in undertaking the neuropsychological assessment and in answering various questions. Participants may experience anxiety and/or claustrophobia when undertaking the MRI. Participants may be inconvenienced by giving up the time required to participate in the research and to recuperate after the treatment session. Participants may be uncomfortable with needles and/or having blood drawn or may experience minor pain at the time of needle insertion.

Minimising risk: Propranolol use

All relevant research team members will have the skills needed for responding to a hypotensive event and Cardiopulmonary resuscitation. Research assistants and other staff members will be required to have a current CPR certification. We will ensure that participants are provided with an accurate and fair description of the risks or discomforts and the anticipated benefits. These are outlined in the RPIS and PICF (see Appendix A and B). The Thompson Institute is appropriately equipped to accommodate participants who are nauseous, vomiting or dizzy.

During referral, acceptance, treatment, and follow-up phases we will assess participants to determine if they pose imminent risk to themselves or others. If so, participants will be referred for immediate intervention and withdrawn from the study.

Minimising risk: Psychological

To mitigate any negative effects of the study measures, care will be taken when administering questionnaires and measures. If any stress or discomfort is observed the participant will be given the option of taking a break and returning to the test/questionnaire later. Where significant distress occurs, we may enlist the assistance of an on-site clinician to assist with reducing discomfort/stress as needed.

If psychological effects are experienced, relevant staff are trained to minimise distress quickly and effectively to participants. This can include de-escalation, psychoeducation, reassurance, implementing a relaxation procedure, grounding methods, and other treatments.

If a potential participant is identified as too vulnerable or fragile to partake in the study, they will not be allowed to be part of it. If a participant becomes vulnerable or fragile during the study, they will be discontinued. This decision will be conveyed to them by a senior staff member in a professional and caring manner.

If any participant indicates they are experiencing a high level of stress or emotional distress, or if they exhibit behaviours suggesting that they are going through a stressful time, we will confirm if this is related to the research or other life events. Irrespective of the cause the mental health clinicians will provide support or referral to assist them to gain stability. To accomplish this, we may need to (with the participant's consent) contact a family member, a referring source, or a member of the health care team treating them for further advice/support. We may need to provide information regarding independent psychological or social services or refer the participant to an independent mental health practitioner.

We will regularly monitor the participants to be aware of any potential for emotional exhaustion, feeling overwhelmed, or worsening of their mental state during the study as they may be under risk of re-experiencing or revealing potential past psychological traumas, or at risk of exacerbating their psychological symptoms. A suitably qualified member of the research team may engage the participants in therapeutic strategies to reduce discomfort/stress as needed.

Minimising risk: Discomfort and inconvenience

The neuropsychological assessments will be scored by a qualified clinician. Self-rated scales may be completed in the presence of research staff. These scales are an integral part of the research, and the perceived benefits outweigh the risks. Before the questions on the scales are asked, we will advise participants that they are welcome to initiate a break at any time if they are anxious or feel discomfort answering the questions.

In instances of claustrophobia or where the participant has indicated distress/discomfort during the MRI, an eye mask will be available, and the participant will be closely monitored. Our senior MRI radiographers have extensive experience in dealing with anxious participants.

Minimising risk: Economic

We will attempt to ensure that the research does not cause social or financial risks or loss to participants. If participants are disadvantaged financially in terms of cost of transportation during research participation, petrol vouchers can be provided. Any payments made to participants (for participating in the assessments) will not adversely influence the design, conduct, findings or publication of the research.

Mandatory reporting

All staff at TI are required to complete mandatory training every two years (at a minimum) in relation to child safety. The [Child Protection Act 1999](#) requires certain professionals (mandatory reporters), to make a report to Child Safety, if they have a reasonable suspicion that a child has suffered, is suffering or is at an unacceptable risk of suffering significant harm caused by physical or sexual abuse, and may not have a parent able and/or willing to protect them. The following plan will be implemented to manage information that triggers mandatory reporting requirements.

1. All medical officers and registered nurses undergo annual mandatory training on Queensland's mandatory reporting requirements as outlined by the Department of Children, Youth Justice and Multicultural Affairs. This training covers recognising reportable incidents, understanding the legal obligations, and the process for reporting.

2. A clear reporting pathway will ensure a prompt notification to the appropriate authorities. A medical officer or registered nurse will, as soon as possible inform [name] (co-investigator and designated safeguarding officer) upon identifying information that may necessitate mandatory reporting. It will be determined if this information constitutes a 'reasonable suspicion' and if so, a report will be made to Child Safety on [name].
3. Any information flagged for mandatory reporting will be documented appropriately, maintaining confidentiality and sensitivity toward the participant's privacy. Only the necessary information required for reporting will be shared with authorities.
4. Team members exposed to potentially distressing information will have access to support resources to manage the emotional impact.

5.8 Potential Study Benefits

Potential benefits to participants taking part in the study include:

- The treatment will impose positive effects on the participant and reduce PTSD symptoms
- The feedback and data collected will assist in evaluating the clinical utility of the treatment.

5.9 Data Collection/Gathering

The study will be collecting mental health information, biospecimens and neurological information of its participants. Collection will take place on site at the UniSC Thompson Institute campus by trained research personnel. The RPIS, consent form, and questionnaire measures will be created in and delivered via Qualtrics, using the research team's password protected UniSC Qualtrics account. Qualtrics is a UniSC approved site and stored survey answers can only be accessed using the researcher's password-protected USC-Qualtrics account.

5.10 Data Management and analysis

Once completed, screening for the total number of completed surveys will take place and we will ensure no personal details (names, contact details etc) are associated with the survey information. All data collected will be stored in line with the UniSC Research Data Management Procedures.

A unique code will be generated for each participant enrolled in the study to de-identify data. The information for linking unique codes to participant contact information will be made accessible to necessary project staff for the purposes of scheduling assessments. All electronic data will be stored securely on computers at the TI/NPRC or on secure research specific databases. Only researchers will have access to the data and other research documents. The computers will be secured by usernames and passwords and protected from external access. Hard copy documents, material, and data will be kept in a locked filing cabinet, inside a locked office. All paper records will be securely converted to pdf files to mitigate the risk of data loss through an emergency (e.g. fire or flood).

Re-identifiable data (using the unique code identifiers) will be exported from Qualtrics to IBM SPSS for analysis. Statistical analyses will include generalised linear models (GLMs), analysis of the relative change index and frequentist statistics. A significance level of $p < .05$ (two-sided test) will be utilised where required. Data will be inspected for outliers and any spurious data will be corrected or removed prior to analysis. A detailed data analysis plan will be constructed by a statistician including the research questions and variables included. Missing data will be examined for missingness patterns. If the data is missing at random or completely at random, data imputation strategies may be employed in order to protect the integrity of this longitudinal sample and statistical power. Data will be analysed using descriptive, bivariate, and multivariate statistics using intent-to-treat analyses.

All material will be kept for at least 15 years from the publication of results, as per national requirements, and then disposed of using secure destruction methods such as shredding of paper data and erasure of computer-generated data. Our main priority will be the protection of participants' confidentiality and the compliance with their informed consents. No participants will be identifiable in abstracts, oral presentations, posters, manuscripts, trial reports, or documents. If a participant requests that their data is withdrawn, the research team will ensure their data is appropriately located and removed.

Biospecimens will be stored in the Thompson Institute/National PTSD Research Centre molecular biology laboratory. Access to the lab is strictly restricted and controlled by UniSC security. Samples will be tested for genetic and expressed/circulating markers using established molecular biology techniques and under the approval of UniSC risk assessments. Any unused sample from a test will be disposed of through approved UniSC biohazard waste disposal protocols (incineration via an established service provider). Biospecimens are labelled with deidentified IDs and processed anonymously in the laboratory setting, with no identifiable information associated with the biospecimens during routine handling or disposal to respect personal and cultural sensitivities. The master document containing identifiable information will be stored in secure UniSC servers and be password protected. The RPIS contains a comment section that allows for any personal or cultural sensitivities relating to biospecimen handling to be captured and implemented by the research team.

Biospecimens are labelled with deidentified IDs and processed anonymously in the laboratory setting, with no identifiable information associated with the biospecimens during routine handling or disposal. The master document containing identifiable information will be stored in secure UniSC servers and be password protected. Only authorised study staff will have access to the identifiable master document. The research being conducted with these biospecimens has no diagnostic value and results will not impact participants health decisions or those of their relatives or community.

Any research collaboration regarding these biospecimens or the data generated from them will require a formal collaborative agreement with UniSC and UniSC ethics and guidelines will govern biospecimen management.

Participants are free to withdraw consent at any time, for any reason. Any biospecimen material remaining at the time of withdrawal will be destroyed as per waste disposal guidelines. Any data generated prior to the withdrawal of consent that is identifiable will be destroyed/deleted. However, data that has been deidentified and aggregated for analysis prior to withdrawal of consent cannot be reidentified and removed at this point, so that data will remain within the analysis in an unidentifiable manner. There are no financial or personal interests to be gained by participants in this study regarding their biospecimens. There are no commercial applications expected from this research.

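### The consent-withdrawal procedure is the default exit for participants who discontinue, and data destroyed on withdrawal carry no exemption for adverse-event or PCL-5 records, so these may be selectively lost

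*Protocol*

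**What the plan says.** **Exit route (Protocol 5.5).** Participants who discontinue are asked for their reasons and about adverse events. Then: "If possible, they will be seen and assessed by an" "Investigator and complete the withdrawal of informed consent procedure". The sentence covers discontinuation in general. Revocation of consent appears later in 5.5, as one of two separate withdrawal criteria.

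**Fate of the data (Protocol 5.10).** Two rules apply:
- On withdrawal of consent: "Any data generated prior to the withdrawal of consent that is identifiable will be destroyed/deleted". The exception is that "data that has been deidentified and aggregated for analysis prior to withdrawal of consent cannot be reidentified and removed at this point".
- On request: "If a participant requests that their data is withdrawn, the research team will ensure their data is appropriately located and removed".

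**State of the data.** The Project Design table in Section 5 labels data identifiable at collection, re-identifiable in storage and non-identifiable at publication. Section 5.10 adds: "Re-identifiable data (using the unique code identifiers) will be exported from Qualtrics to IBM SPSS for analysis".

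**Duties that assume the data still exist.** Section 5.10 promises intent-to-treat analyses and retention of all material for at least 15 years after publication. Section 5.5 says: "Adverse events will be followed up until resolution, the adverse event stabilises, or the participant is lost to follow up". Appendix I requires every adverse event on the case report form with supporting source documents, follow-up reports for serious events, and continued contact about events unresolved at withdrawal.

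**The concern.** Stopping treatment, stopping assessments and revoking consent to the use of data are three different acts. Section 5.5 blurs them by placing the consent-withdrawal step inside the general discontinuation paragraph, and 5.10 attaches destruction of data to it.

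The loss would not be random. Under 5.5, participants are discontinued if they develop complications or become too vulnerable, and participation is withdrawn after an adverse reaction that does not need an ambulance. Section 5.7 adds withdrawal for imminent risk to self or others. Those sent towards the consent-withdrawal form are therefore likely to include a disproportionate share of those harmed or worsening. The study has a single arm (5.1), so no comparator would reveal the gap.

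At stake are the adverse-event proportion, the pre-discontinuation PCL-5 scores that intent-to-treat needs, and the ability to match serious-event reports held by the ethics committee to source records. Deletion cannot be undone, so no analysis plan can repair it.

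**Working it through.** The protocol gives no figure on this point, so the check is mainly textual.

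**Step 1: who reaches the procedure.** Discontinuers in general, qualified by where possible. It is a default, not a universal rule.

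**Step 2: what is destroyed.** The 5.10 exception needs two conditions together, de-identified and aggregated, and its stated reason is that such data cannot be traced back. Coded participant-level data can be traced through the code link, so that reason points to their destruction. The word used in the rule, however, is *identifiable*, and the design table calls stored data *re-identifiable*. The text does not settle which applies.

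**Step 3: what is exempt.** Nothing visible exempts adverse-event, serious-event, case report form or PCL-5 records from either rule. Section 5.3 says analysis runs throughout the study, so some data could be aggregated before a participant leaves, but no schedule is given.

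**Step 4: can all the duties be met?** If coded data are destroyed, intent-to-treat analysis, 15-year retention of all material, source documentation of every adverse event and serious-event follow-up reporting cannot all be honoured for that participant.

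**Step 5: illustration.** Only N = 150 (5.2) comes from the protocol. Discontinuation and event rates are assumed, and every discontinuer's record is taken as deleted (worst case). With d discontinuers and event proportions p_c in completers and p_d in discontinuers:
- true proportion = [(150 − d)·p_c + d·p_d] / 150
- reported proportion = p_c
- share of participants with an event who are lost = d·p_d / [(150 − d)·p_c + d·p_d]

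Central case, d = 30, p_c = 10%, p_d = 30%: (120 × 0.10 + 30 × 0.30)/150 = (12 + 9)/150 = 14%, reported as 10%. Share lost = 9/21 = 43%.

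Range at p_c = 10%:

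| d | p_d | True | Reported | Share lost |
|---|---|---|---|---|
| 15 | 10% | (13.5 + 1.5)/150 = 10% | 10% | 1.5/15 = 10% |
| 30 | 30% | 14% | 10% | 43% |
| 45 | 50% | (10.5 + 22.5)/150 = 22% | 10% | 22.5/33 = 68% |

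The ratio of true to reported runs from 1.0 to 2.2. With p_c = 2% and p_d = 20% instead, d = 15 gives (2.7 + 3)/150 = 3.8% and d = 45 gives (2.1 + 9)/150 = 7.4%, both reported as 2.0%: ratios of 1.9 and 3.7. The size is therefore set by the assumptions. If no records are deleted, the bias is zero.

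Precision is a lesser matter. The one-sided 95% upper bound for an event never seen, 1 − 0.05^(1/n), moves from 2.0% at n = 150 to 2.8% at n = 105.

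**The case against.** A reader might infer that every discontinuing participant has their data destroyed and that harms are thereby erased. The documents do not support that.

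- The 5.5 step applies only where possible, and revocation of consent is listed separately. The escalation text withdraws participation, not consent.
- The destruction sentence follows several paragraphs on biospecimens and could be meant for specimen-derived data, with other study data removed only on request. This is a coherent reading. Against it, specimen material has its own sentence, the next one speaks of any data, and the on-request rule stands before the biospecimen text and covers a participant's data without limit.
- Coded data may not count as identifiable. That stands as an ambiguity; the exception for aggregated data pulls the other way.
- Serious events will already have been reported to the ethics committee within 24–48 hours (Appendix I), and aggregated data remain. This narrows the loss to participant-level records, mainly non-serious events and outcome scores.
- The consent form that 5.5 cites is not in the reviewed text and may settle what happens to collected data.

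A reader might also quote a two- to four-fold understatement of harms. That follows from assumed rates and complete deletion, not from anything in the protocol.

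What remains is that the consent step sits in the discontinuation paragraph and no visible text protects safety or outcome records.

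**Conclusion.** The concern holds as a conflict in the protocol's wording with a real route to selective loss. Followed literally, 5.5 and 5.10 can remove participant-level adverse events and PCL-5 scores from people who stop, often because of harm, contrary to the protocol's own intent-to-treat, retention and safety-documentation statements. This rests on coded data being treated as identifiable, on the destruction rule reaching beyond biospecimen-derived data, and on the unseen consent form not saying otherwise. The on-request removal rule leaves a narrower version of the problem even if the first two fail.

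The size cannot be derived from the protocol. In the illustration with 10% of completers having an event, a true 10–22% is reported as 10%, and 10–68% of participants with an event disappear, all under the worst case of complete deletion. Because deletion is irreversible and the repair is wording, it should be settled before further participants consent.

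**What to change.** 1. **Protocol 5.5:** separate stopping treatment sessions or study visits from revoking consent, and use the consent-withdrawal procedure only for revocation. The discontinuation criteria themselves need not change for this.
2. **Protocol 5.10:** state that coded data collected up to that point, including adverse-event and serious-event records and PCL-5 scores, are retained and analysed as far as consent and law allow; that safety records are exempt from deletion; and that leftover biospecimens are destroyed. Say whether *identifiable* includes coded, re-identifiable data.
3. **Protocol 5.10, on-request removal:** reconcile this rule with the retained data and with the 15-year retention rule. Cutting the removal right down to optional items such as video is a debatable trade-off and is not needed.
4. **Consent form:** check its text first, then align it.

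The cost is one ethics amendment. The downside is that the limit on erasing trial data must be explained at consent.
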